**Protocol Number: 20170596** 

**Date:** 20 May 2019 Page **59 of 132** 

# 7.4.1.1.2 Guidelines for Hematologic Toxicity

Guidelines for carfilzomib dose modification in the event of thrombocytopenia and neutropenia are summarized in Table 7-3.

Table 7-3. Dose Modification Guidelines for Thrombocytopenia and Neutropenia

Hematologic toxicity	Recommended Action		
Thrombocytopenia			
When platelets fall to < 30 x 10  /L and for each subsequent drop to < 30 x 10  /L  Neutropenia	If platelets 10 to 30 x 109/L without evidence of bleeding	
 
hold
 
restart at previous dose when platelets > 30 x 10^9/L
 
	
	If evidence of bleeding or platelets < 10 x 10  /L	
 
hold
 
restart at 1 dose decrement when platelets > 30 x 10^9/L
 
	
When ANC falls to < 0.75 x 10  /L and for each subsequent drop to < 0.75 x 10  /L	If ANC 0.5 to 0.75 x 109/L	continue at full dose	
	If ANC < 0.5 x 10  /L	
 
hold dose
 
resume at 1 dose decrement when ANC ≥ 0.5 x 10^9/L
 
	

ANC = absolute neutrophil count.

# 7.4.1.1.3 Guidelines of Nonhematologic Toxicity

Guidelines for dose modification in the event of nonhematologic toxicities are summarized in Table 7-4.

**Protocol Number: 20170596** 

**Date**: 20 May 2019 Page **60 of 132** 

Table 7-4. Dose Modification Guidelines for Nonhematologic Toxicities

For grading criteria, see CTCAE grading scale in Section 12.4.			
Symptom/Sign/Investigation	Recommended Action		
Renal Dysfunctiona:			
Estimated GFR ≥ 15 mL/min/1.73 m 	Full dose. For acute deterioration requiring dialysis, see below.		
Estimated GFR < 15 mL/min/1.73 m  (NCI-CTCAE grade 4)	Hold dose until estimated GFR returns to ≥ 15 mL/min/1.73 m², then resume same dose. If dialysis is required (regardless of estimated GFR levels), use the maximal dose of 20 mg/m² and administer carfilzomib after dialysis.		
Chronic dialysis stable for ≥ 30 days	Dose may be re-escalated up to full dose as clinically tolerated (see Section 7.4.1.1.4. for dose re-escalation). Carfilzomib must be administered after dialysis.		
Hepatic Dysfunction and Related Investi	gations		
Mild to moderate liver dysfunction:	25% dose reduction.		
defined as 2 consecutive values, at least 28 days apart, of: (1) total bilirubin (> 33% direct) > 1x ULN to < 3x ULN OR	Dose may be re-escalated if liver function tests return to normal and drug-induced hepatotoxicity is excluded.		
(2) an elevation of AST and/or ALT with normal bilirubin			
Grade 3 elevation in bilirubin (> 3x ULN), ALT and/or AST (> 5x ULN)	Hold carfilzomib until resolution to baseline or normal.  Monitor any abnormality weekly. Resume carfilzomib with a 25% dose reduction for 1 full cycle if drug-induced hepatotoxicity is excluded. If no worsening in the total bilirubin, AST or ALT on the reduced dose for 1 full cycle, dose may be re-escalated, if drug induced hepatotoxicity is excluded (see Section 7.4.1.1.4 for dose re-escalation instructions).		
Drug-induced hepatotoxicity (attributable to carfilzomib)	Discontinue carfilzomib.		
Other Nonhematologic Toxicities			
Tumor lysis syndrome: 3 or more of the following:  • increase in creatinine of ≥ 50%  • increase in uric acid of ≥ 50%  • increase in phosphate of ≥ 50%  • increase in potassium of ≥ 30%  • decrease in calcium OR  • increase in LDH of ≥ 2-fold from baseline	Hold carfilzomib until all abnormalities in serum chemistries have resolved; resume at full dose.		
	Page 1 of '		

Page 1 of 3

Footnotes defined on last page of this table.

**Protocol Number: 20170596** 

**Date**: 20 May 2019 Page 61 of 132

Table 7-4. Dose Modification Guidelines for Nonhematologic Toxicities

For grading criteria, see CTCAE grading scale in Section 12.4.			
Symptom/Sign/Investigation	Recommended Action		
Congestive heart failure	Any subject with congestive heart failure, whether or not drug related, must have the dose held until resolution or return to baseline. Appropriate medical management should be initiated. Once congestive heart failure resolves or returns to baseline, treatment may continue at 1 dose level reduction. If no resolution after 4 weeks, the subject will be withdrawn from all study treatment.		
Infection (grade 3 or 4)	Hold carfilzomib. Once infection is controlled and the subject is without infection-related symptoms, and if ANC > $1.0 \times 10^9$ /L, resume at full dose. If ANC < $1.0 \times 10^9$ /L, follow hematologic toxicities dose reduction guidelines.		
Neuropathy (grade 2 with pain, or grade 3)	Hold carfilzomib until resolved to ≤ grade 2 without pain; then resume at 1 dose decrement.		
Neuropathy (grade 4)	Permanently discontinue carfilzomib.		
Dyspnea (grade ≥ 3)	Hold carfilzomib until resolution to grade 1 or baseline, then resume at 1 dose decrement. Investigate cause and record findings. If caused by another adverse event listed in this table, follow recommendations for that adverse event.		
Hypertension (SBP > 140 and/or DBP >	90, measured per Section 12.15)		
< Grade 3	Continue at same dose if initiation of appropriate treatment controls hypertension (see Section 12.12 for guidance)		
Grade ≥ 3	Hold carfilzomib until resolution to normal or baseline. Initiate appropriate anti-hypertensive therapy prior to resuming carfilzomib at 1 dose decrement (see Section 12.12 for guidance).		
Pulmonary toxicity:  Non-infectious interstitial lung disease, acute respiratory failure, ARDS (≥ grade 3)	Hold carfilzomib until resolution to grade 1 or baseline and restart at 1 dose decrement.		
Pulmonary hypertension (grade ≥ 3)	Hold carfilzomib until resolution to grade 1 or baseline and restart at 1 dose decrement		
Posterior reversible encephalopathy syndrome: Headaches, altered mental status, seizures, visual loss, and hypertension	If PRES is suspected, hold carfilzomib. Consider evaluation with neuroradiological imaging, specifically MRI, for onset of visual or neurological symptoms suggestive of PRES. If PRES is confirmed, permanently discontinue carfilzomib. If the diagnosis of PRES is excluded, carfilzomib administration may resume at same dose, if clinically appropriate.		
Thrombotic microangiopathy: Fever, microangiopathic hemolytic anemia, renal failure, thrombocytopenia, neurological manifestations	If the diagnosis is suspected, hold carfilzomib and manage per standard of care including plasma exchange as clinically appropriate. If TMA is confirmed, permanently discontinue carfilzomib. If the diagnosis is excluded, carfilzomib can be restarted at prior dose		

Page 2 of 3

Footnotes defined on last page of this table.

Protocol Number: 20170596

**Date:** 20 May 2019 Page 62 of 132

Table 7-4. Dose Modification Guidelines for Nonhematologic Toxicities

For grading criteria, see CTCAE grading scale in Section 12.4.		
Symptom/Sign/Investigation	Recommended Action	
Venous thrombosis (≥ grade 3)	Hold carfilzomib and adjust anticoagulation regimen; resume at full dose once anticoagulation has been optimized per treating investigator's discretion.	
Any other drug-related nonhematologic toxicity ≥ grade 3 b	For carfilzomib attribution, hold dose. Resume at 1 dose decrement when toxicity has resolved to grade 1 or less or to baseline grade.	

Page 3 of 3

ALT = alanine aminotransferase; ANC = absolute neutrophil count; ARDS = acute respiratory distress syndrome; AST = aspartate aminotransferase; CTCAE = Common Terminology Criteria for Adverse Events; DBP = diastolic blood pressure; GFR = Glomerular Filtration Rate; LDH = lactate dehydrogenase; MRI = magnetic resonance imaging; NCI-CTCAE = National Cancer Institute-Common Terminology Criteria for Adverse Events; PRES = Posterior Reversible Encephalopathy Syndrome; SBP = systolic blood pressure; TMA = thrombotic microangiopathy; ULN = upper limit of normal.

# 7.4.1.1.4 Rules for Re-escalation of Carfilzomib Dose Following Toxicity

Conditions of carfilzomib-related toxicity that are not permitted for dose re-escalation:

- Pulmonary hypertension
- Non-infectious pulmonary toxicities (per Table 7-4)
- Congestive heart failure (≥ grade 3)

A reduction in dose level required for any of the adverse events listed above may not be re-escalated. For all other carfilzomib-related toxicities that require dose level reduction, if the reduced dose level is tolerated for 1 full cycle, carfilzomib may be re-escalated at the treating physician's discretion up to the maximum dose planned in that cycle (56 mg/m² twice weekly or 70 mg/m² once weekly).

# 7.4.1.2 Non-Amgen/Amgen Non-investigational Product: Dexamethasone

The reason for dose change of dexamethasone is to be recorded on each subject's CRF.

For conditions that do not require dexamethasone dose reduction, refer to Section 7.4.1.1.3.

For subjects  $\geq$  75 years of age, the starting dose of dexamethasone should be 20 mg weekly, 10 mg administered on days 1, 2, 8, 9, 15, 16, 22, and 23 during cycles 1-2, and 20 mg administered on the days 1, 8, 15 during cycles 3-12.

<sup>a For a rapid fall from baseline in estimated GFR or an absolute fall of ≥ 60 mL/min/1.73 m², contact the medical monitor.

<sup>b In the event of a possible drug-related nonhematologic toxicity, the investigator should, to the best of his/her ability, assess its relationship to carfilzomib (K), dexamethasone (d), or the combination of Kd to the extent possible. If both carfilzomib and dexamethasone are considered likely to be involved, then recommended actions for both should be instituted.

Protocol Number: 20170596

**Date:** 20 May 2019 Page 63 of 132

## 7.4.1.2.1 Dose Reduction Levels

Two dose reduction levels are defined for dexamethasone, as shown in Table 7-5. Dose reductions are permanent and dose must not be increased following a dose reduction.

Table 7-5. Dose Decrements for Dexamethasone

	Reduced Weekly Dexamethasone Doses (mg)		
Nominal Dose (mg)	Dose -1	Dose -2	
40	20	12ª	
20	12	8	

<sup>a If the dose needs to be divided over 2 days, administer 8 mg on the first day and 4 mg on the second day.

# 7.4.1.2.2 Guidelines for Dexamethasone-related Toxicity

Dexamethasone will be permanently discontinued after 2 dose reductions in the event of additional dexamethasone-related toxicities. At the investigator's discretion, dexamethasone may be tapered prior to complete discontinuation according to institutional practice. The subject may continue on treatment with the other protocol-specified drug(s).

Guidelines for dexamethasone-related toxicities are summarized in Table 7-6.

**Protocol Number: 20170596** 

**Date**: 20 May 2019 Page **64 of 132** 

Table 7-6. Treatment Guidelines for Dexamethasone-related Toxicity

Symptom	Findings	Recommended Action
Cardiovascular	Edema > grade 3 (anasarca or limiting function and unresponsive to therapy)	Diuretics as needed, and restart dexamethasone at 1 dose decrement; if edema persists despite above measures, decrease dose by another dose decrement.  Discontinue dexamethasone permanently if symptoms persist despite second reduction.
Gastrointestinal Toxicity	Dyspepsia, gastric or duodenal ulcer, or gastritis grade 1 or 2 (requiring medical management)	Continue dexamethasone at same dose and treat with therapeutic doses of histamine 2 (H2) blockers, or proton pump inhibitor.
		Consider adding sucralfate or other antiulcer treatment as clinically indicated.
		If symptoms persist despite above measures, decrease dexamethasone dose by 1 dose level.
	Dyspepsia, gastric or duodenal ulcer, or gastritis ≥ grade 3 (requiring hospitalization or surgery)	Hold dexamethasone until symptoms return to baseline.
		Restart dexamethasone at 1 dose decrement along with concurrent therapy with H2 blockers, sucralfate, or omeprazole.
		If symptoms persist despite above measures, discontinue dexamethasone permanently.
	Acute pancreatitis	Discontinue dexamethasone permanently.
General Disorders	Limb edema > grade 3 (> 30% limb discrepancy in volume;	Hold dexamethasone until symptoms return to baseline.
	gross deviation from normal anatomic contour; limiting self-care activities of daily living)	Diuretics as needed, and restart dexamethasone at 1 dose decrement; if edema persists despite above measures, decrease dose by another dose decrement.
		Discontinue dexamethasone permanently if symptoms persist despite second reduction.
Psychiatric Disorders	Confusion or mood alteration ≥ grade 2 (interfering with	Hold dexamethasone until symptoms return to baseline.
	function ± interfering with activities of daily living)	Restart dexamethasone at 1 dose decrement.
		If symptoms persist despite above measures, reduce by another dose decrement.

Page 1 of 2

Protocol Number: 20170596

**Date**: 20 May 2019 **Page 65 of 132** 

Table 7-6. Treatment Guidelines for Dexamethasone-related Toxicity

Symptom	Findings	Recommended Action
Musculoskeletal Muscle weakness ≥ grade 2 (symptomatic and interfering		Decrease dexamethasone by 1 dose decrement.
	with function ± interfering with activities of daily living)	If weakness persists, decrease dose by another dose decrement.
		Discontinue dexamethasone permanently if symptoms persist.
Metabolism and Nutrition Disorders	Hyperglycemia ≥ grade 3 (fasting glucose > 250 mg/dL)	Treat with insulin or other hypoglycemic agents as needed until glucose is ≤ grade 2 (< 250 mg/dL) then resume dexamethasone.
		If uncontrolled despite above measures, decrease dose by 1 dose decrement until ≤ grade 2 (< 250 mg/dL).
All Other	Other toxicity ≥ grade 3 felt related to dexamethasone	Hold dexamethasone dose. Resume at 1 dose decrement when toxicity has resolved to ≤ grade 2.
		If toxicity recurs, hold dexamethasone dose until toxicity has resolved to ≤ grade 2 and resume dexamethasone dose by another dose decrement.
		If toxicity recurs despite 2 dose decrements, discontinue dexamethasone permanently.

Page 2 of 2

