# 7.4.1.3 Conditions Not Requiring Dose Reduction

Carfilzomib and dexamethasone do not need to be held in the following cases:

- grade 3 nausea, vomiting, or diarrhea (that responds within 7 days to adequate treatment of antiemetics and/or antidiarrheal agents)
- grade 3 dexamethasone-related hyperglycemia
- isolated grade 3-gamma-glutamyl transferase elevation
- grade 3 fatigue (unless persisting for > 7 days)
- alopecia

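### For grade 3 dexamethasone-related hyperglycemia, the protocol's dexamethasone rules disagree on whether to hold the drug and, if glucose stays uncontrolled, on whether the decrement is temporary or permanent

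*Protocol*

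**What the plan says.** Four places in the protocol bear on this event.

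- **Section 7.4.1.3.** The heading is "Conditions Not Requiring Dose Reduction". The opening sentence reads "Carfilzomib and dexamethasone do not need to be held in the following cases", and the list includes "grade 3 dexamethasone-related hyperglycemia". Two other entries (nausea, vomiting or diarrhea; fatigue) carry a 7-day qualifier. Hyperglycemia carries none.
- **Section 7.4.1.2.2, Table 7-6, metabolism row.** The trigger is "Hyperglycemia ≥ grade 3 (fasting glucose > 250 mg/dL"), so grade 3 is covered here too. The first action is "Treat with insulin or other hypoglycemic agents as needed until glucose is" grade 2 or lower, after which the site is to resume dexamethasone. The second action, only if glucose is still uncontrolled, is to "decrease dose by 1 dose decrement until" grade 2 or lower.
- **Section 7.4.1.2.1.** "Dose reductions are permanent and dose must not be increased following a dose reduction". No exception is given for hyperglycemia. Table 7-5 sets the first decrement at 40 to 20 mg, or 20 to 12 mg.
- **Section 7.4.1.2.** "For conditions that do not require dexamethasone dose reduction, refer to Section 7.4.1.1.3". Section 7.4.1.1.3 is the carfilzomib nonhematologic toxicity section; the list of exempt conditions is in 7.4.1.3.

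Nothing in the protocol says which text takes precedence.

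**The concern.** Two questions that a site must answer have more than one answer in the text. The first, for any grade 3 dexamethasone-related case, is whether the drug is interrupted. The second, for cases that stay uncontrolled, is whether the decrement is reversed once glucose improves or stays for the rest of treatment.

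The answers feed the primary data. Section 4.1 lists as primary endpoints the ratio of actual to full intended cumulative dose, relative dose intensity, and dose modifications with reasons. Section 10.3.2.3.1 defines the intended dose by reference to sections 7.1.1.2 and 7.1.2, which takes in dexamethasone, and makes no allowance for modifications or skipped doses. SAP section 5 also defines a relative dose intensity for dexamethasone. All three arms receive the drug. With about 75 subjects at about 40 sites, fewer than two per site on average, different sites could well settle on different readings. Part of what is reported as adherence would then reflect which sentence the site followed.

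**Working it through.** **Texts side by side, grade 3 dexamethasone-related event**

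| Question | Section 7.4.1.3 | Table 7-6 | Section 7.4.1.2.1 |
|---|---|---|---|
| Hold? | Not needed | Implied, since the drug is later resumed | Silent |
| Reduce? | Heading says not required | Only if uncontrolled after treatment | Silent |
| Duration of a reduction | Silent | Runs until grade 2 or lower | Permanent |

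Hyperglycemia is the only Table 7-6 row that attaches an end point of this kind to a decrement.

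**Inputs**

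- Planned dexamethasone, under 75 years (section 7.1.2.1): 20 mg on 8 days in each of cycles 1-2, and 40 mg on 3 days in each of cycles 3-12.
- Planned dexamethasone, 75 years or older (section 7.4.1.2): 10 mg and 20 mg on the same days.
- First decrement (Table 7-5): 40 to 20 mg, a cut of 20/40 = 50%; 20 to 12 mg, a cut of 8/20 = 40%.
- Assumptions: one uncontrolled event at the start of the stated cycle, all 12 cycles completed, all other doses given, and held doses not made up.

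**Planned total**

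2 × 8 × 20 + 10 × 3 × 40 = 320 + 1200 = 1520 mg. For age 75 or older the total is half of that, 760 mg.

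**Share of intended dose, 40 mg nominal**

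- No hold and no cut: 1520/1520 = 100%.
- One weekly dose held: (1520 − 40)/1520 = 97.4%.
- Decrement for one cycle, then restored: (1520 − 3 × 20)/1520 = 1460/1520 = 96.1%.
- Permanent from cycle 4 (9 cycles, 27 doses): (1520 − 27 × 20)/1520 = 980/1520 = 64.5%.
- Permanent from cycle 9 (4 cycles, 12 doses): (1520 − 12 × 20)/1520 = 1280/1520 = 84.2%.

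**Share of intended dose, 20 mg nominal**

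- One-cycle decrement: (760 − 3 × 8)/760 = 96.8%.
- Permanent from cycle 9: (760 − 12 × 8)/760 = 87.4%.

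**Effect on an arm mean, permanent versus one-cycle handling, 40 mg nominal**

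The documents give no rate of uncontrolled hyperglycemia, so 2 to 5 of 25 subjects per arm is assumed.

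- Cycle 4: gap (540 − 60)/1520 = 31.6 points per subject; × 2/25 = 2.5 and × 5/25 = 6.3 points.
- Cycle 9: gap (240 − 60)/1520 = 11.8 points per subject; × 2/25 = 0.9 and × 5/25 = 2.4 points.

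For scale only, protocol section 10.1 expects 95% confidence interval half-widths of 2.0 to 5.9 points for mean relative dose intensity. That precision argument is built around carfilzomib, so it is a rough yardstick here.

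**The case against.** The best case for the plan is that this is loose wording with a workable reading.

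- **The hold.** Section 7.4.1.3 is permissive: saying the drug need not be held does not forbid holding it. Table 7-6 gives recommended actions, and its hyperglycemia row never orders a hold, although several other rows do. This stands as far as it goes. It means that neither reading breaches the protocol, which is why two sites may act differently.
- **The decrement.** No sentence says that the dose is restored, and re-escalation rules exist for carfilzomib only (section 7.4.1.1.4). The row could mean stepping down until control is reached, which would agree with section 7.4.1.2.1. That reading is possible. The time-limited one is more natural, and the text does not settle the matter.
- **The cross-reference.** It is wrong, but section 7.4.1.3 directly follows Table 7-6 and names dexamethasone. A reader might infer that sites following the reference would never find the exemption; the documents do not show that.
- **Endpoint impact.** The analysis is descriptive, with no test or threshold to cross, and SAP section 9.6.9 does not list relative dose intensity among its dexamethasone exposure summaries. This limits the consequence. The dose ratio and the dose modifications are still primary.

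Two further inferences are not supported. One is that a site which reverses the cut has not used up a reduction: section 7.4.1.2.2 counts reductions towards permanent discontinuation and makes no exception. The other is that grade 4 has conflicting rules: section 7.4.1.3 is limited to grade 3, so only the Table 7-6 row applies to grade 4.

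**Conclusion.** The inconsistency is real and worth correcting. Hold or no hold is unclear for every grade 3 dexamethasone-related case. Temporary or permanent is unclear only for cases that stay uncontrolled after treatment.

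A reader might infer that any grade 3 episode could leave the dose untouched or halve it for good. The documents do not support that: Table 7-6 reaches the decrement only after treatment has failed, and a halving applies only to the 40 mg nominal dose.

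Within the uncontrolled subset, the choice is between 96.1% of intended dexamethasone and 64.5% (cycle 4) or 84.2% (cycle 9) for one subject on 40 mg. The shift in an arm mean, 0.9 to 2.4 points for cycle 9 events and 2.5 to 6.3 points for cycle 4 events, rests on an assumed 2 to 5 uncontrolled cases among 25, all on 40 mg and completing 12 cycles, and on every site taking one reading rather than the other. Rarer or later events would make it smaller. This is an internal inconsistency that affects conduct and descriptive primary data; it does not undermine the design.

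**What to change.** Reconcile section 7.4.1.3 (heading and list), the hyperglycemia row of Table 7-6, and section 7.4.1.2.1. The text should give one answer to each of two questions: whether grade 3 dexamethasone-related hyperglycemia calls for a hold or a reduction, and whether the decrement in that row is permanent. Which clinical rule applies is for the sponsor to decide; this review takes no position on it. Correct the reference in section 7.4.1.2 so that it points to section 7.4.1.3.

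The cost is a table row, a sentence or two and one cross-reference, in an amendment or a site clarification. No new data collection is needed. If subjects have already been handled under differing readings, the recorded reasons for dose change can be used to identify and describe those cases in the report.

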# 7.4.1.3 Conditions Not Requiring Dose Reduction

Carfilzomib and dexamethasone do not need to be held in the following cases:

- grade 3 nausea, vomiting, or diarrhea (that responds within 7 days to adequate treatment of antiemetics and/or antidiarrheal agents)
- grade 3 dexamethasone-related hyperglycemia
- isolated grade 3-gamma-glutamyl transferase elevation
- grade 3 fatigue (unless persisting for > 7 days)
- alopecia

# 7.4.1.4 Non-Amgen Non-investigational Product: Lenalidomide

Lenalidomide may be discontinued, temporarily delayed, or dosage temporarily reduced, in the event of a treatment-related toxicity that, in the opinion of the investigator, warrants the discontinuation, temporary delay or dose reduction. Investigators are advised to consult the approved regional labeling for lenalidomide for additional details.

The reason for dose change of lenalidomide is to be recorded on each subject's eCRF.

Protocol Number: 20170596

**Date:** 20 May 2019 **Page 66 of 132** 

# 7.4.1.5 Non-Amgen Non-investigational Product: Pomalidomide

Pomalidomide may be discontinued, temporarily delayed, or dosage temporarily reduced, in the event of a treatment-related toxicity that, in the opinion of the investigator, warrants the discontinuation, temporary delay or dose reduction. Investigators are advised to consult the approved regional labeling for pomalidomide for additional details.

The reason for dose change of pomalidomide is to be recorded on each subject's eCRF.

